1. BACKGROUND AND RATIONALE

Beta-lactams (penicillins, cephalosporins, carbapenems and aztreonam) are the most commonly prescribed antibiotics [1] as these agents have large therapeutic window, avoiding the need for therapeutic drug monitoring, and are associated with lower adverse effects compared to other antimicrobials. Despite their widespread usage, there are emerging evidence that suggest current licensed beta-lactam doses may be suboptimal and irrelevant to clinical practice, especially in the setting of rising antimicrobial resistance and variable/unpredictable pharmacokinetic changes in specific patient groups [2-8]. Thus, therapeutic drug monitoring (TDM) to optimise and individualise beta-lactam dosing regimens has been suggested [2-6].

Beta-lactam TDM will be increasingly important in the following areas:

1. Use of high dose beta-lactam therapy to treat resistant infections

Antimicrobial resistance is a known public health threat. A national surveillance study in Singapore from 2006-2007 found increased incidence of multi-drug resistant bacteria, including resistance to one of the broadest spectrum antibiotic class, carbapenems [9-11]. Since then, antimicrobial resistance has been noted to be increasing exponentially [12-16]. In fact, carbapenem resistance rates among common Gram-negative bacteria, are reported to be around 10 to 50% locally [13]. Such resistant infections place a significant burden on healthcare, as they increase morbidity, mortality, resource utilisation and costs [17,18]. Globally, it is predicted to cause 300 million premature deaths and cost SGD 150 trillion by 2050 [18].

Optimal treatment for resistant bacterial infections is limited. Currently available alternative antibiotics, such as tigecycline, polymyxin B and aminoglycosides, are often associated with adverse effects such as hepatotoxicity and nephrotoxicity. In addition, pathogens with multidrug resistance could already be resistant to these agents [19]. Unfortunately, very few novel antibiotics are available in the pipeline and for the newly approved agents (e.g. ceftolazone/tazobactam), resistance is already being reported [20]. These novel agents are also significantly costlier than currently available antibiotics. In such desperate situations, prescribers may need to resort to high dose beta-lactam therapy, often exceeding current licensed recommendations, to achieve beta-lactam levels beyond the elevated minimum inhibitory concentrations (MIC) of the resistant pathogens to ensure maximum bacterial kill and efficacy [3,21]. This implies that doses of beta-lactams used would be at or near the threshold for adverse effects or toxicity and the concept of wide therapeutic window for beta-lactams no longer applies. In order to balance between efficacy and toxicity in such setting, beta-lactam TDM with subsequent dose adjustment would be required to ensure optimal therapy. This will also give prescribers confidence to use such high dose beta-lactam regimens.

2. Use of high dose beta-lactam therapy to treat pathogens with "intermediate" susceptibility

The Clinical and Laboratory Standards Institute (CLSI) and the European Committee on Antimicrobial Susceptibility Testing (EUCAST) are shifting towards reclassifying pathogens with intermediate beta-lactam susceptibility to susceptible-dose-dependent (SDD) or susceptible, increased exposure, respectively [22,23]. This implies that high dose beta-lactam therapy can still be used to treat pathogens with "intermediate" beta-lactam susceptibility. Only beta-lactam TDM will enable us to ensure that the high dose beta-lactams dosage regimens are sufficient for such infections while avoiding risks for toxicity. If high dose beta-lactam therapy

could be used with confidence in these situations, we can avoid unnecessary switch to other agents, which may be more broad-spectrum, toxic or expensive. This will allow us to reserve the use of these antibiotics for highly resistant pathogens.

3. Use of pharmacokinetic/pharmacodynamics-guided approach to individualise and optimise beta-lactam therapy

Current "one-size-fits-all" beta-lactam dosing regimens are largely derived from Phase I clinical studies on healthy volunteers. They may be sub-optimal in clinical practice as patients may display variable and unpredictable pharmacokinetics, for example, those who are critically ill [4,5], febrile neutropaenia [8], burns [28], with renal/liver impairment [29], or require dialysis and other extracorporeal therapies [30]. In fact, studies have shown that conventional beta-lactam dosing recommendations were unable to achieve therapeutic targets in at least 35-50% in these patients [4,5,8,30], requiring further dose adjustments guided by beta-lactam TDM [5,28]. Hence, dose individualisation using TDM is increasingly being advocated.

In addition, technology in dialysis is rapidly evolving with new generation filters, dialysis techniques/modes being developed and placed in clinical practice [31]. However, their effects on beta-lactam disposition and clearance are limited (e.g. limited publication available for plasmapheresis, molecular adsorbent recirculating system therapy). More importantly, in Singapore General Hospital, dialysis filters have now switched from low flux to high flux membranes as the default for most patients. Some studies have reported increased clearance with high flux dialysis for small drug molecules, such as beta-lactams, resulting in reduced antimicrobial exposure with conventional renally-adjusted dosing regimens [32] and potentially affect clinical outcomes. Hence, beta-lactam TDM will be increasingly important in these patients. We would also like to elucidate from this study how these changes in dialysis technology would influence our beta-lactam dosing regimens.

Evidence Gap with Beta-lactam TDM:

Beta-lactam TDM is only performed in a few centres worldwide. Outside Japan, no other Asian countries are reported to perform beta-lactam TDM routinely. As there could be pharmacokinetic/pharmacodynamic differences between Asian and Caucasian populations due to differences in ethnicity, clinical practice (e.g. types and settings of dialyser machines/membranes) and resistance patterns of pathogens, we hope this study could provide early insights to generate recommendations most suitable for our local/Asian population and setting.

In addition, therapeutic targets for beta-lactam TDM are not well established, with varying practices world-wide [33]. None the beta-lactam targets have been extensively clinically validated. Beta-lactams exhibit time-dependent bactericidal activity and their pharmacokinetic/pharmacodynamics therapeutic target is characterised by the percentage of the dosing interval for which the unbound beta-lactam concentration is maintained above the MIC (fT>MIC). Based on in vitro and in vivo studies, the targets are 40% of the dosing interval (40% fT>MIC) for carbapenems, 50% (50% fT>MIC) for penicillins and 60-70% (60-70%) fT>MIC) for cephalosporins [34-36]. However, clinical observational studies suggest a longer fT>MIC for optimal clinical outcomes (mortality, clinical response, duration of hospital stay) [4,37-39]. In addition, some studies have shown that higher plasma concentrations (fT>4- $5 \times MIC$) may be required for maximal bactericidal activity [40-41], optimal tissue penetration [42-44], optimal clinical response and microbial eradication in patients with pneumonia [45] and

prevention of resistance [6,46]. Centres, that perform beta-lactam TDM, have used the targets 100%fT>MIC, 40-70%fT>4-5xMIC (depending on type of beta-lactam) or 100%fT>4-5xMIC [33] but no studies have compared these targets in terms of clinical outcomes achieved. In this study, we plan to evaluate the correlation between beta-lactam target and clinical outcomes and to determine which beta-lactam target is optimal for clinical practice.

To address the gaps in evidence above, we propose a prospective observational study to evaluate the feasibility of beta-lactam TDM in the local setting. Our target population will be adult patients (21 years old and above), admitted to Singapore General Hospital, are receiving beta-lactams for documented or suspected infection and belong to the following group of patients who will most benefit from beta-lactam TDM: i.e. critically ill patients (admitted to intensive care units, intensive care areas, high dependency wards), haematology/oncology patients, burns patients, patients with extracorporeal therapies which will alter beta-lactam pharmacokinetics (e.g. extracorporeal membrane oxygenation, dialysis), patients with resistant infections or deep-seated infections requiring high dose beta-lactam therapy and patients, who are suspected or at risk of developing beta-lactam adverse effects. We will prospectively collect four blood samples over a dosing interval from each patient. The beta-lactam levels will be assayed using liquid chromatography with tandem mass spectrometry. Attending physicians will have the option of knowing the results and whether to accept dose adjustments recommendations by trained infectious disease pharmacist. Proportion of patients attaining therapeutic targets during the first and subsequent TDM will be evaluated. Patients will also be followed up for clinical outcomes such as mortality and clinical response.

2. HYPOTHESIS AND OBJECTIVES

We hypothesise that current licensed beta-lactam dosing regimens are suboptimal in at least half our patients: patients with severe sepsis in intensive care units/high dependency wards, burns patients, patients requiring dialysis and other forms of extracorporeal therapy, haematology/oncology patients, and patients with resistant pathogens or deep-seated infections requiring high dose beta-lactam therapy. Hence, beta-lactam TDM would be necessary for these patients to optimise their dosing regimens and improve their clinical outcomes.

Our primary objective is to evaluate proportion of sub-optimal beta-lactam levels in correlation to MIC and the need for dose adjustments

Our secondary objectives include:

- 1. Correlating the achieved pharmacokinetic/pharmacodynamic therapeutic targets (100%T>MIC, 40-70%T>5xMIC, 100%T>5xMIC) with clinical outcomes (mortality, clinical response, microbial eradication) in the different sub-groups mentioned above
- 2. Characterising beta-lactam pharmacokinetics (as exploratory analysis) for certain patient populations, with limited beta-lactam pharmacokinetics characterised in primary literature (e.g. those requiring extracorporeal therapy, various types of dialysis), to aid design of empiric dosing regimens suitable for local practice.

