4. STUDY POPULATION

4.1. List the number and nature of subjects to be enrolled.

Patients will be recruited until 320 assays are performed (based on budget of \$40,000, estimated cost of each assay is \$125, number of assays = 40,000/125 = 320 assays). This will be roughly equivalent to 80 patients, assuming patients will have 4 assays each. There will be no restriction on race or gender.

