For all patients, 4 sets of blood samples (5 mL each) will be obtained via venipuncture or existing cannula access within a dosing interval. We propose to obtain 4 samples for each TDM in this study to generate more robust and accurate drug concentration-time curves for calculation of target attainment and to better characterise patients' pharmacokinetic profiles. For most patients (except those on intermittent extracorporeal therapies), blood samples will be obtained during end of infusion, 1 hour after infusion, 2 hours after infusion and within 30 minutes of the next scheduled dose (i.e. trough level) if beta-lactam is given as short infusion over \leq 30 minutes. If beta-lactam is given as extended infusion (e.g. 3-4 hours), blood samples will be obtained at mid-infusion, end of infusion, 1 hour after infusion and within 30 minutes of the next scheduled dose (i.e. trough level). For patients on intermittent extracorporeal therapies (e.g. intermittent dialysis), blood samples will be obtained at end of beta-lactam infusion, at the beginning of dialysis, end of dialysis and within 30 minutes of the next scheduled dose (i.e. trough level).

To ensure therapeutic targets are reached, further blood sampling, according to the schedule above, may be performed after dose adjustments or when there is a change in patient's clinical status (e.g. change in dialysis settings, change in renal function), which may warrant change in beta-lactam dosing regimen. Blood sampling for TDM will be stopped when beta-lactam has been discontinued, when therapeutic targets are achieved or when patient has been discharged from the hospital.

Assay of beta-lactam levels

All blood samples will be sent to our research laboratory for assay via liquid chromatographytandem mass spectrometry. All blood samples will be labelled by our study team using subject codes (no patient identifiers will be used).

Beta-lactam TDM and Dose Individualisation

The treating physicians will have the option to know the results of the TDM, once available. An infectious disease-trained pharmacist may make recommendations on dose adjustments based on the TDM results. However, accepting these recommendations will be at the discretion of the treating physicians.

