8. SAMPLE SIZE AND STATISTICAL METHODS

8.1. Determination of Sample Size

Patients will be recruited until 320 assays are performed (based on budget of \$40,000, estimated cost of each assay is \$125, number of assays = 40,000/125 = 320 assays). This will be roughly equivalent to 80 patients, assuming patients will have 4 assays each.

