8.2. Statistical and Analytical Plans

Our primary outcome will be attainment of beta-lactam therapeutic targets: 100%fT>MIC, 40-70%fT>5xMIC, 100%fT>5xMIC. Proportion of patients, who achieve beta-lactam therapeutic targets, during the first and subsequent TDM will be determined. For the group of patients, who require dose adjustments, after the 1st TDM and need further TDM, the proportion of patients who require dose increment and dose reduction, the number of TDM performed to achieve therapeutic target and the mean/median time required to achieve therapeutic target will also be evaluated.

Correlation of primary outcomes will be made to the following secondary outcomes.

- a. Mortality at the end of therapy and within 30-day mortality.
- b. Days to defervescence
- c. Days to resolution of white blood cell count, pro-calcitonin and C-reactive protein.

Any incidence of adverse effects related to beta-lactam therapy will also be reported and evaluated in correlation to beta-lactam levels.

For univariate analyses with binomial outcomes (e.g. mortality), Chi-square test or Fisher's exact test will be performed where appropriate. For univariate analyses with time-dependent outcomes (e.g. days to defervescence, days to resolution of inflammatory markers), Kaplan-Meier analysis will be performed. For univariate analyses with continuous outcome variables (e.g. APACHE II score, SOFA score), Student's t-test and Mann-Whitney-U test will be performed for parametric and non-parametric data respectively. Multivariate analyses will then be performed to include potential confounders such as APACHE II score, SOFA score, Charlson comorbidity index, use of beta-lactam as culture-directed therapy, presence of multi-drug resistant infection, and presence of concurrent infections requiring additional antibiotics. Logistic regression will be used for binomial outcomes (mortality) while Cox regression will be used for time-dependent outcomes (days to defervescence, days to resolution of inflammatory markers).

To evaluate population pharmacokinetics in various patient groups, a specialised pharmacokinetic software will be used to develop population pharmacokinetic models. Model simulation will then be performed to design empiric dosing recommendations to guide local practice.

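### Dosing recommendations for local practice are to be simulated from exploratory pharmacokinetic models on at most about 80 patients, with no plan to carry parameter uncertainty

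*Combined protocol and SAP*

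**What the plan says.** Section 2 lists pharmacokinetic characterisation as secondary objective 2. It marks the work as exploratory, limits it to populations that are poorly described in the literature, and gives its purpose as "to aid design of empiric dosing regimens suitable for local practice". Section 8.2 says that specialised software will be used to develop population models, and then: "Model simulation will then be performed to design empiric dosing recommendations to guide local practice".

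The sample size is a budget figure: "number of assays = 40,000/125 = 320 assays" (Section 8.1), and "This will be roughly equivalent to 80 patients, assuming patients will have 4 assays each" (Sections 4.1 and 8.1). Section 5 takes "4 sets of blood samples (5 mL each) will be obtained via venipuncture or existing cannula access within a dosing interval" and adds that "further blood sampling, according to the schedule above, may be performed after dose adjustments". Those repeat samples draw on the same 320 assays.

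No single drug is chosen. Section 1 defines the class as "Beta-lactams (penicillins, cephalosporins, carbapenems and aztreonam"), and the inclusion criteria in Section 4.3 admit any beta-lactam across several overlapping patient groups. The documents give no number of patients per drug or population, no pooling rule, no attainment threshold for accepting a regimen, no model validation and no statement about parameter uncertainty.

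**The concern.** A fitted population model gives estimates of the typical clearance and of the spread between patients. Simulating from those estimates as if they were exact treats both as known. When a regimen is then chosen because the simulated attainment just reaches a threshold, estimation error works against the patients: the chosen regimen attains the target less often, on average, than the figure reported for it. The smaller the number of patients behind the model, the larger the gap, and a bare point estimate of attainment would not reveal it.

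The output is intended for the groups that the protocol thinks may be under-dosed, including dialysis and other extracorporeal therapy. There is also a mismatch that needs no calculation: work labelled exploratory in Section 2 ends in Section 8.2 as recommendations for practice.

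**Working it through.** **The plan's own figure.** 40,000 / 125 = 320 assays; 320 / 4 = 80 patients. Both reproduce. This is budget arithmetic, not a precision calculation.

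**How many patients could stand behind a model.** If a share r of patients has one repeat set of 4 samples, N = 320 / (4 × (1 + r)).
- r = 0: N = 80.
- r = 0.5: N = 320 / 6 = 53. Half is only a proxy, taken from the hypothesis that "current licensed beta-lactam dosing regimens are suboptimal in at least half our patients".
- r = 1: N = 40.

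The split by drug and population is not stated, so I used a range of n per model. As illustrations only: 80 / 4 classes = 20; an even split over 4 classes and the 5 populations of the hypothesis gives 80 / 20 = 4.

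**Shortfall under plug-in simulation with selection.** Assumptions that are not in the documents: the required exposure is log-normal between patients; each patient's parameters are known without error (a best case); the regimen is set where the fitted model predicts 90% attainment. On the log scale the regimen sits at the estimated mean plus 1.2816 estimated SDs. Expected true attainment is then

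T(n−1)[1.2816 / √(1 + 1/n)],

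where T(n−1) is the t distribution function on n − 1 degrees of freedom. The size of the between-patient variability cancels out.

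| n | Argument | Expected true attainment | With maximum-likelihood SD |
|---|---|---|---|
| 4 | 1.146 | 83.3% | 80.3% |
| 5 | 1.170 | 84.7% | 82.3% |
| 8 | 1.208 | 86.7% | 85.2% |
| 10 | 1.222 | 87.4% | 86.2% |
| 20 | 1.251 | 88.7% | 88.1% |

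Simulation of the same model agrees. The share of selected regimens with true attainment below 80% is 32% at n = 4, 21% at n = 8 and 8% at n = 20.

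**Where the loss comes from (n = 4).** The expected SD estimate is 0.92 of the true SD, so the log-scale percentile is low by 1.2816 × 0.08 ≈ 0.10 SD. That alone gives 88.1%, a loss of 1.9 points. The other 4.8 points, down to 83.3%, are scatter in the estimates averaged through a curved function. The median true attainment is 87.6%, and 43% of selected regimens reach 90% or more.

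**Sensitivity to the selection rule (n = 5).**
- One-compartment model, full-interval target, clearance CV 30–70%, volume CV 30%, regimen set exactly at 90%: true attainment 85.2–86.4%; 23–27% of regimens truly below 80%.
- Same model, regimens restricted to a two-fold ladder: claimed 92.1–93.7%, true 87.6–90.8%.
- Fixed regimen, not selected on the data, true attainment 90%, in the log-normal model: mean plug-in estimate 89.2% (unbiased SD) or 90.9% (maximum-likelihood SD). Almost no bias.

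**With uncertainty carried.** Replace 1.2816 by t(0.9, n−1) × √(1 + 1/n). At n = 4 this is 1.638 × 1.118 = 1.83; at n = 10 it is 1.45. Expected attainment is then 90.0% at every n in the log-normal model, and 91.6–92.7% at n = 5 in the one-compartment model.

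**The case against.** The strongest reply is that the plan is silent rather than wrong. Section 8.2 does not say that point estimates will be simulated, names no 90% threshold and does not commit to a separate model per population. A population model can pool groups with covariates, and with 20 patients the average shortfall is only about 1 point. The work is already labelled exploratory, no primary conclusion rests on it, and simulation detail is often left to a separate modelling plan. All of this stands, and it makes the shortfall conditional.

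Three stronger readings are tempting, and the documents do not support them.
- A reader might infer that every model will rest on about 4 patients. That needs an even split over a grid the plan never describes. The populations overlap, one of them is defined by pathogen and infection rather than by pharmacokinetics, and objective 2 covers only certain populations.
- A reader might infer that recommended regimens will under-attain. That follows only if point estimates are used and the regimen is selected on the fitted model.
- A reader might infer that the upper tail of clearance is systematically underestimated. On the clearance scale at n = 4 the mean estimated 90th percentile is 0.99, 1.01 and 1.04 times the true value at CVs of 30%, 50% and 70%.

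The reply does not remove two things. Designing regimens from a simulation is a form of selection on the fitted model. And recommendations that guide practice claim more than an exploratory analysis does.

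**Conclusion.** The point holds in conditional form. The plan goes from models fitted to at most about 80 patients, on an unstated mix of drugs and populations, to recommendations for practice, with no stated handling of parameter uncertainty. If point estimates are simulated and a regimen is selected at a predicted 90%, true attainment would average about 83–87% with 4 to 10 patients per model and about 89% with 20. The figures rest on the assumed threshold, log-normal variability and individual parameters known without error. A coarser choice of regimens narrows the gap, and without selection on the data it nearly disappears. The mismatch between the exploratory label and the practice-guiding output depends on none of these assumptions. The primary outcome is not affected.

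**What to change.** In Section 8.2:
1. In each simulation, draw the model parameters, including between-patient variance, from their bootstrap or estimated uncertainty distribution.
2. Report each probability of target attainment with a 95% interval and the number of patients behind it.
3. Describe the outputs as candidate regimens for prospective evaluation, in line with the exploratory label in objective 2.

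This needs wording and some extra computing, and no further patients or assays. It calibrates the reported figure but adds no information. Intervals will be wide where few patients contribute, and some drugs may yield no usable regimen. With very few patients a bootstrap is itself only approximate, which is a further reason to show the patient count. No dose or regimen is proposed here.
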